6.1.6. Treatment naïve / experienced patients

Treatment naïve (First Line) patients:

Patients who have not received any conventional treatment for pHLH. In treatment-naïve patients, an initial background therapy of 10 mg/m2 dexamethasone will be required. Dexamethasone not more than 7 days or Methylprednisolone pulses for less than 3 consecutive days until emapalumab treatment start (SD0).

Treatment experienced (Second line) patients:

Patients who have received conventional HLH therapy (as per site standard of care), e.g., any of the following alone or in combination (Etoposide, ATG, Alemtuzumab and Cyclosporine A) and Dexamethasone at 10 mg/m2 for more than 7 days or methylprednisolone pulses for 3 or more consecutive days before emapalumab treatment start (SD0).

The following derivation to identify second line patients will be done:

• Yes to Question: Was any HLH treatment administered at diagnosis [History of HLH treatments]

and

- Medication that:
 - Contains text 'HLH 2004'.

or

- Medication recorded in eCRF with a start date prior to emapalumab first infusion as follows: (priorities need to be followed as below list, check first condition first if not met then check second condition, if not met then the third and so on).

o Etoposide [ATC04ID L01CB - Preferred code 00511901001], any dose, any duration o Antithymocyte immunoglobulin [ATC04ID L04AA - Preferred code 00575401001], any dose, any duration

o Alemtuzumab [ATC04ID L04AA - Preferred code 01268601001], any dose, any duration

o Cyclosporin A [ATC04ID L04AD - Preferred code 00549701001], any dose, any duration

o Anakinra [ATC04ID L04AC - Preferred code 01345101001], any dose, any duration o Tocilizumab [ATC04ID L04AC - Preferred code 01759101001], any dose, any duration

o Dexamethasone [ATC04ID H02AB - Preferred code 00016001001], dose ≥ 10 mg/m² for at least 7 days

[figure not shown]
o Methylprednisolone [ATC04ID H02AB - Preferred code 00049601001], with a verbatim indicating "pulses" or "high dose", or any dose for more than 7 days or 30 mg/kg for 3 consecutive days

and any of the following

- Having not achieved a satisfactory response (Unsatisfactory response)
- Having not responded or worsened (No response or worsening)
- Showing intolerance to previous conventional treatment of HLH.
- Having reactivated after satisfactory response based on investigator assessment at screening.

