At present, no drug, other than emapalumab (in the USA), is approved for the treatment of pHLH. Most commonly used conventional therapy for the initial treatment of pHLH and severe forms of sHLH is immunochemotherapy. Hematopoietic stem cell transplantation (HSCT) is required to cure pHLH and is indicated in forms (independently of the trigger, if known) of HLH which appear recurrent or progressive despite intensive therapy, or which present central nervous system (CNS) involvement (Jordan 2004). It has been shown that a reduction or abrogation of signs of HLH activity prior to HSCT is an important step in order to improve HSCT outcome and survival.

The most commonly used immunochemotherapy is the so called HLH-94 regimen which includes the use of high doses of dexamethasone and etoposide. The results of prospective study of this regimen, initially published by (Henter 2002) and subsequently by (Trottestam 2011) showed a 5-year cumulative probability of survival of 54%.

In an attempt to improve survival, two alternative treatment regimens have been proposed and assessed: the HLH-2004 one based on addition of cyclosporine A to the HLH-94 treatment protocol (Henter 2007), and the treatment investigated in the 'HIT-HLH' study (Hybrid Immunotherapy for HLH) combining treatment with anti-thymocyte globulin (ATG), etoposide and dexamethasone.

Despite these more aggressive immunochemotherapies, no significant improvement in mortality was obtained with either of the two regimens, as reported at the latest Histiocyte Society meeting in October 2016 (Henter for the HLH-2004 study oral presentation, Jordan 2016 for the HIT-HLH study).

A significant number of patients with HLH either fail to respond to current therapies or relapse prior to HSCT. Furthermore, withdrawal of the drugs commonly used for the treatment of HLH may be required due to their toxicities (e.g., severe infections, myelosuppression, malignant hypertension), thus leaving HLH patients without alternative treatment options and significantly increasing the risk of death. No conventional salvage therapy is available at present, although the use of rescue alemtuzumab has been reported in a retrospective series of 22 patients (Marsh 2013).

Study NI-0501-09 NI-0501 in Primary HLH Page 26 of 92

With mortality and morbidity remaining high, the scientific community concurs that new therapeutic approaches are needed.

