3.6 STUDY COMMITTEES

An Independent Data Monitoring Committee (iDMC) has overall responsibility for safeguarding the interests of subjects by monitoring relevant data obtained in the study and making appropriate recommendations based on the reported data, thus ensuring that the study is being conducted with the highest scientific and ethical standards. Moreover, the iDMC will be specifically tasked with regular assessment of extent of benefit and fatal events prior to transplant in the treatment-naïve subgroup of patients.

iDMC operations will be described in the iDMC charter.

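### The second-line derivation in SAP 6.1.6 requires HLH treatment at diagnosis, so a patient first treated later but before emapalumab is not identified as treatment-experienced

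*SAP*

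**What the plan says.** SAP 6.1.6 first describes the two groups in words. Treatment-experienced patients are those who received conventional HLH therapy before Study Day 0; naive patients are those who received none, apart from short glucocorticoid exposure. SAP 6.1.7 and Protocol section 4 describe experience in the same general way. None of these texts says when, relative to diagnosis, the earlier therapy must have been given.

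SAP 6.1.6 then gives a programmable rule for second-line patients. Its conditions are joined by 'and':

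- **A.** "Yes to Question: Was any HLH treatment administered at diagnosis [History of HLH treatments".
- **B.** A medication that satisfies one of two branches joined by 'or'. Branch B1 is "Contains text 'HLH 2004". Branch B2 is "Medication recorded in eCRF with a start date prior to emapalumab first infusion as follows", followed by eight drugs, among them "Etoposide [ATC04ID L01CB - Preferred code 00511901001], any dose, any duration", "Cyclosporin A [ATC04ID L04AD - Preferred code 00549701001], any dose, any duration" and "Dexamethasone [ATC04ID H02AB - Preferred code 00016001001], dose ≥ 10 mg/m² for at least 7 days".
- **C.** Unsatisfactory response, no response or worsening, intolerance, or reactivation.

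On regimens, Protocol 1.1 states: "The most commonly used immunochemotherapy is the so called HLH-94 regimen". It also names HLH-2004 (with a hyphen) and HIT-HLH.

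**The concern.** The programmable rule is narrower than the definition it is meant to implement. Condition A ties experience to treatment at diagnosis; the definitions ask only whether conventional therapy was given before emapalumab. A gap between diagnosis and first treatment is foreseeable, because inclusion criterion 2 accepts a molecular diagnosis or a consistent family history. Protocol 8.1 also has sites record any conventional HLH therapy previously received, so the broader information is collected.

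Branch B1 raises a second, smaller doubt. A text search is useful when a site enters a regimen name instead of individual drugs, yet it looks for one name in one spelling.

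Naive versus experienced is the only split specified in SAP 6.1.7. Table 3 applies it to the primary and secondary endpoints, the sensitivity analyses, exposure, quality of life and safety. Neither Table 3 nor the disposition categories in SAP 7.1 has a place for an unclassified patient. The pre-lock data review meeting in SAP section 5 is specified for membership of the analysis sets, not for subgroup assignment.

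**Working it through.** The plan gives no figure to reproduce here, so the check is to apply the rule literally to test records and compare the result with the definitions.

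**Rule.** Second-line = A and (B1 or B2) and C. Condition C is taken as met throughout.

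| Treatment at diagnosis (A) | Medication record | B1 | B2 | Second-line by the rule |
|---|---|---|---|---|
| Yes | Text HLH 2004 | met | not met | yes |
| Yes | Text HLH-2004 only | not met | not met | no |
| Yes | Text HLH-94 only | not met | not met | no |
| Yes | HLH-94, with etoposide and qualifying dexamethasone entered | not met | met | yes |
| Yes | HLH-2004, with etoposide and cyclosporin A entered | not met | met | yes |
| No | Etoposide started after diagnosis, before first infusion | not met | met | no |
| No | Text HLH 2004 | met | not met | no |

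An entry reading only HIT-HLH behaves like the third row.

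**Against the definitions.** The last two rows show the main conflict. The patient with etoposide before the first infusion has received conventional therapy under SAP 6.1.6, SAP 6.1.7 and Protocol section 4, and meets B2, yet A alone removes him or her.

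**Extent of the text problem.** By Protocol 1.1, HLH-94 includes dexamethasone and etoposide, HLH-2004 adds cyclosporine A, and HIT-HLH combines ATG, etoposide and dexamethasone. Etoposide, ATG and cyclosporin A are in B2 at any dose and duration, and dexamethasone is there with a dose and duration threshold. With A and C met, a patient on any of these regimens is therefore found once a qualifying component is recorded under a listed code. Only entries with nothing but a regimen name are missed.

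**Illustrative size.** The documents give no subgroup counts. Assume 17 patients per group, with 12/17 = 70.6% responders among naive and 10/17 = 58.8% among experienced. If m pretreated non-responders are counted as naive, the rates become 12/(17 + m) and 10/(17 − m):

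- m = 1: 12/18 = 66.7% and 10/16 = 62.5%
- m = 2: 12/19 = 63.2% and 10/15 = 66.7%
- m = 3: 12/20 = 60.0% and 10/14 = 71.4%

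If the two moved patients were responders, the gap would widen: (12 + 2)/19 = 73.7% and (10 − 2)/15 = 53.3%. If two non-responders were left unassigned instead, naive would stay at 70.6% and experienced would become 10/15 = 66.7%.

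**The case against.** **The drug list does most of the work.** A reader might infer that the derivation recognises prior therapy only through the string HLH 2004, so that HLH-94 patients are lost. The documents do not support that: branch B2 finds them through their component drugs, and no document shows that regimen-only entries exist. This objection stands and confines the text problem to a secondary gap.

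**The eCRF is not shown.** The question in condition A sits under the history of HLH treatments, and sites may answer it with all earlier therapy in mind. The stored spelling of regimen names is also unknown. This stands as a limit on frequency. It does not reconcile the wording of the rule with the definitions.

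**Missed patients need not become naive.** It is tempting to infer that they do. But SAP 6.1.6 defines naive separately, as having received no conventional treatment, and a patient with recorded etoposide fails that too. The supported statement is that such a patient is either unassigned or placed in the naive group against the definition.

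**Consequences elsewhere.** The iDMC is tasked with "regular assessment of extent of benefit and fatal events prior to transplant in the treatment-naïve subgroup of patients", and SAP 7.2 sets different dexamethasone requirements for naive and second-line patients. A reader might infer that both inherit the error. The documents do not say so: iDMC operations are left to a charter, and deviations are classified after medical review, with no stated link to this derivation.

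**Noise and visibility.** With about 17 patients per group, exact 95% intervals in the illustration are 44–90% versus 33–82% before two patients move and 38–84% versus 38–88% after, so the reversed order is well within chance. No test of naive against experienced is planned. Previous HLH treatments are tabulated and listed (Table 14.1.5, Listing 16.2.4.3), so an error could be noticed. These points stand, but noticing an error at reporting is no substitute for a rule that matches its definition.

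**Conclusion.** The rule is wrong as written, in a limited way. Condition A contradicts the plan's own definitions: read literally, therapy begun after diagnosis but before the first emapalumab infusion does not make a patient second-line, whatever drug is recorded. Branch B1 adds a smaller gap, confined to records that hold only HLH-2004, HLH-94 or HIT-HLH with no listed component drug entered.

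What is at risk is the naive/experienced displays in Table 3. The primary test is safe, because SAP 8.1 defines the response rate on the All Treated total, which does not depend on the split. The number of affected patients is unknown. The illustration rests on assumed counts; it shows that one to three reassigned patients can shift subgroup rates by several percentage points in either direction, not that they will. The conclusion rests on reading the 'and' and the quoted string literally, as a programmer would.

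**What to change.** In SAP 6.1.6:

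1. Replace the at-diagnosis condition with any HLH treatment recorded in History of HLH Treatments or the CM module with a start date before the first emapalumab infusion. This also gives the text branch a date limit, which it now lacks.
2. Keep the coded drug list and the response, intolerance or reactivation condition unchanged. Keeping the list leaves the treatment of anakinra and tocilizumab as the SAP now codes it.
3. Match regimen text regardless of case and separator for HLH-94 or HLH-1994, HLH-2004 and HIT-HLH.
4. Add confirmation of each treated patient's subgroup to the data review meeting before database lock, so that nobody is left unassigned.

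The cost is a few lines of SAP text, a revised text search and one review of the treatment histories of at most 41 patients (the enrolment maximum in Protocol 11.1). No new data are needed.

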16.2. Concomitant Medications for HSCT Conditioning

Table 19: Concomitant HSCT Conditioning Medication Preferred Terms

ATC Level 4	Preferred Code	Preferred Text
L01AA	00021101001	CYCLOPHOSPHAMIDE
201121	00006401001	MELPHALAN
L01AB	00036801001	BUSULFAN
	00418901001	TREOSULFAN
L01AC	00053501001	ТНІОТЕРА
L01BB	02122001001	CLOFARABINE
LUIDD	01004601001	FLUDARABINE
	01004602001	FLUDARABINE PHOSPHATE
L01BC	00146201001	CYTARABINE
L01BC	00511901001	ETOPOSIDE
20120	00511902001	ETOPOSIDE PHOSPHATE
L01XC	01402501001	RITUXIMAB
L04AA	01268601001	ALEMTUZUMAB
Lonni	00575401001	ANTITHYMOCYTE IMMUNOGLOBULIN
	00575402001	ANTITHYMOCYTE IMMUNOGLOBULIN (RABBIT)
	02082701001	ANTILYMPHOCYTE IMMUNOGLOBULIN

16.3. Disease Indicating Central Nervous System (CNS) Involvement / CSF abnormalities by Medical History/AE Preferred Term and Code

[figure not shown]
Preferred Term Code	Preferred Term
10029818	Nuclear magnetic resonance imaging brain abnormal
10059703	CSF test abnormal
10053805	CSF white blood cell count increased
10011522	CSF cell count increased
10035551	Pleocytosis
10012559	Developmental delay
10056832	Neurological examination abnormal
10047641	VIth nerve paralysis
10020745	Hyperreflexia
10041962	Status epilepticus
10039906	Seizure
10021118	Hypotonia
10002948	Aphasia
10029202	Nervous system disorder
10017577	Gait disturbance
10048334	Mobility decreased
10008096	Cerebral atrophy
10015037	Epilepsy
10071066	Posterior reversible encephalopathy syndrome
10022840	Intraventricular haemorrhage

The overall response criterion 'No neurological and CSF abnormalities attributed to HLH' is not fulfilled during the time period in which any of the above listed AEs is present or the assessment on neurological examination CRF is 'abnormal' with comment 'CNS involvement'.

AD-ST-33.06 Effective date: 12-Nov-2020

Statistical Analysis Plan, Sponsor Sobi AG

Protocol Number NI-0501-09 PCN Number 176784

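### The SAP 6.1.6 codes for prior etoposide and ATG omit etoposide phosphate and rabbit ATG, so a pretreated patient can fail to be derived as second-line

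*SAP*

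**What the plan says.** SAP 6.1.6 derives second-line status from three conditions that must all hold: HLH treatment was given at diagnosis; a qualifying medication is recorded; and the outcome was an unsatisfactory response, no response or worsening, intolerance, or reactivation.

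The medication condition is met by the free text HLH 2004 or by a listed drug started before the first infusion. The list is worked through in order ("priorities need to be followed as below list, check first condition first if not met then check second condition"). The two entries at issue are "Etoposide [ATC04ID L01CB - Preferred code 00511901001", likewise accepted at any dose and duration, and "Antithymocyte immunoglobulin [ATC04ID L04AA - Preferred code 00575401001], any dose, any duration". The others are alemtuzumab, cyclosporin A, anakinra and tocilizumab at any dose, and rules for dexamethasone and methylprednisolone.

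SAP Table 19 (Appendix 16.2), written to identify HSCT conditioning drugs, has separate rows for "ETOPOSIDE PHOSPHATE" under 00511902001 and for "ANTITHYMOCYTE IMMUNOGLOBULIN (RABBIT" under 00575402001.

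In words, SAP 6.1.6 defines a naive patient as one who has had no conventional pHLH treatment. SAP 6.1.7 and Protocol section 4 name etoposide and ATG as conventional therapy without restricting salt or animal source. SAP 6.1.7 and Table 3 then split nearly every analysis by this status.

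**The concern.** The rule accepts etoposide and ATG at any dose for any duration, so the intent is plainly that any exposure counts. The codes are narrower than that intent. Table 19 shows that the coding dictionary keeps these two forms apart from the parent terms, so a search on the parent code alone will not return them.

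The SAP deals with this problem elsewhere. The glucocorticoid tapering rules in Table 14 (SAP 6.1.9.4) list three hydrocortisone codes and require manual checks of salt derivatives for triamcinolone and cortisone. SAP 6.1.6 has no comparable safeguard.

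At stake is who sits in the naive and experienced columns. With at most 41 patients enrolled (SAP 3.2), each column is small, and one or two misplaced patients would move its response rate visibly.

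**Working it through.** The plan gives no figure to reproduce; the check compares codes and then traces the logic.

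**1. Codes for the same drugs in the two lists**

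| Term | Code | In 6.1.6 | In Table 19 |
|---|---|---|---|
| Etoposide | 00511901001 | yes | yes |
| Etoposide phosphate | 00511902001 | no | yes |
| Antithymocyte immunoglobulin | 00575401001 | yes | yes |
| Antithymocyte immunoglobulin, rabbit | 00575402001 | no | yes |
| Alemtuzumab | 01268601001 | yes | yes |

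**2. Trace of the derivation.** Second-line = A and B and C, where A is treatment at diagnosis, B the medication condition and C the outcome condition. Take a patient with A and C true whose prior therapy is coded 00511902001 or 00575402001. B is still true if any one of these holds:

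- the text HLH 2004 is recorded;
- alemtuzumab, cyclosporin A, anakinra or tocilizumab was given;
- dexamethasone was given at 10 mg/m² or more for at least 7 days;
- methylprednisolone was recorded as pulses or high dose, or given at any dose for more than 7 days, or at 30 mg/kg for 3 consecutive days.

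If none holds, B is false and the patient is not second-line. With the two codes added, B is true and the patient is second-line.

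**3. Where the missed patient goes.** The naive subgroup in 6.1.7 refers back to 6.1.6, where the only programmed derivation is the one for second-line. If naive is programmed as its complement, the patient is analysed as naive. If naive is applied as worded, the patient is neither naive nor second-line. Both outcomes conflict with the definitions.

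**4. How complete the other routes are.** Protocol 1.1 describes etoposide given with high-dose dexamethasone, and ATG given with etoposide and dexamethasone, so many such patients would still be caught. The routes have gaps, however. The text search is for HLH 2004, whereas the protocol hyphenates the name and calls HLH-94, which also contains etoposide, the most commonly used regimen; a literal search could miss either. Intolerance to earlier therapy is an entry route (Protocol 4.1.1), and a patient who stopped early may not have reached 7 days of dexamethasone at the stated dose.

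**5. Illustration of size.** The documents give no subgroup counts. Assume, for illustration only, a correctly defined naive group of 10 with 7 responders (7/10 = 70.0%). Patients wrongly added change this as follows:

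- one responder: 8/11 = 72.7%, up 2.7 points;
- one non-responder: 7/11 = 63.6%, down 6.4 points;
- two non-responders: 7/12 = 58.3%, down 11.7 points.

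The experienced column would lose the same patients. If no patient is affected, the shift is zero.

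**The case against.** The strongest reply is that the gap may never bite. A patient must miss every other route, and the usual regimens supply several of them. US enrolment is limited to treatment-naive patients (Protocol section 4), which shrinks the pretreated pool. A misplacement could also be seen: prior HLH treatments are tabulated (Table 14.1.5) and listed (Listing 16.2.4.3), and Table 3 shows prior therapies by naive and experienced columns. All of this stands, and it is why the number at risk may be zero. But being able to notice an error in a listing is not a specified correction, and the rule as written still departs from the SAP's definitions.

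A reader might infer more than the documents support:

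- **That a missed patient is certainly classed as naive, or that short steroid exposure alone suffices.** The SAP never states that naive is the complement of the derivation, and steroid duration is only one of several routes.
- **That the two lists place etoposide in conflicting ATC groups.** The ATC column of Table 19 is visibly garbled as read from the PDF, so no conclusion can rest on it.
- **That iDMC review of the naive subgroup is compromised.** Protocol 3.6 leaves iDMC operations to its charter, and nothing says that the committee uses this derivation.
- **That antilymphocyte immunoglobulin (02082701001), also only in Table 19, is wrongly omitted.** Neither document names it as conventional HLH therapy.

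**Conclusion.** The point holds in limited form. SAP 6.1.6 states a selection rule that, followed literally, misses patients whose prior etoposide or ATG is coded to a form that the SAP itself lists separately. Such a patient would be analysed as naive or drop out of both groups.

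This rests on two assumptions: that the preferred codes are matched exactly as listed, and that the patient meets no other route. The number affected is unknown and may be zero. The primary exact binomial test uses the total All Treated Analysis Set (SAP 8.1) and does not change. The exposure is confined to the naive and experienced columns of Table 3, where in a group of about 10 one patient would shift the response rate by roughly 3 to 6 points under the illustrative counts. It should be corrected because the rule contradicts the stated definitions and the repair is nearly free.

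**What to change.** In SAP 6.1.6, add 00511902001 to the etoposide entry and 00575402001 to the ATG entry. Alternatively, select prior therapy by active ingredient, with a manual check of salt and source variants like the one already required in the glucocorticoid rules of Table 14. Before database lock, check every patient not derived as second-line against Listing 16.2.4.3 (History of HLH Treatments), and state in 6.1.6 whether naive is the complement of second-line.

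The cost is two codes, a sentence or two of SAP text, and a review of at most 41 patients. No new data are needed.
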